### Prohibited Medications for SmartPill

1. No medications which may alter gastric pH around the time of the study, which includes:
  - a. Proton Pump Inhibitors for 1 week (examples: omeprazole, lansoprazole and esomeprazole, pantoprazole, rabeprazole)
  - b. Histamine2 Blockers for 3 days [(examples: cimetidine (Tagamet HB), famotidine (Pepcid), and ranitidine hydrochloride (Zantac), nizatidine (Axid)]

- c. Antacids for 1 day (examples: Maalox, Mylanta, Amphogel, Tums, Rolaids)
2. No medications that affect gastrointestinal motility for 3 full days before the start of the study and during the 5 ensuing days of study including but not limited to those drugs listed below:
  - a. Prokinetic agents, such as metoclopramide (Reglan), tegaserod (Zelnorm), domperidone (Motilium), erythromycin, zithromycin, cisapride
  - b. Anti-emetics agents, such as phenergan, compazine
  - c. Narcotic analgesic agents, such as methadone, fentanyl, percocet
  - d. Anticholinergic agents for IBS – Bentyl, Levsin
  - e. Medications for constipation, including enemas, cathartics, polyethylene glycol solutions (including Miralax), and lactulose (e.g., enulose). Patients with constipation may take medications to help stimulate a bowel movement with either milk of magnesia, 2.4 to 4.8 grams (30-60 ml), or magnesium citrate, 11 to 25 grams daily in 1 or more doses, up to 48 hours prior to SmartPill ingestion.
  - f. 5HT3 antagonists, such as Lotronex (alosetron hydrochloride) and Zofran (ondansetron hydrochloride).
  - g. Anti-diarrheal agents, such as Kaopectate (attapulgit, donnagel, rheaban), Pepto-Bismol (bismuth subsalicylate), Imodium (loperamide), and lomotil (atropine diphenoxylate).
  - h. Opiate agents used to treat diarrhea.

#### Permitted Medications for SmartPill

1. NSAIDs (examples: Aspirin, Advil, Motrin) may be used
2. Acetaminophen may be used.
3. Prescription medications for maintenance of stabilized conditions (e.g., hyperlipidemia, chronic anxiety, birth control, etc) with drugs such as anti-hyperlipidemics (e.g., HCG Co-A reductase inhibitors, Lipitor); antidepressants (e.g., Prozac, etc) are permitted if the condition and the dose are stable for six months prior to enrolment in the study.

#### **Recruitment Procedures**

Patients will be recruited via the Massachusetts General Hospital lysosomal storage disease clinic. The study will be presented to all patients with Fabry disease who have had gastrointestinal symptoms within the past year. Additionally, we will contact physicians who care for Fabry patients via email and conferences to inform them of the study. If patients indicate they are interested in the study to their provider, the patient may be contacted if the provider refers the patient to the study staff. Flyers with the research coordinator's contact information will also be given to interested patients and providers at conferences. At conferences, if interested, patients will be given the opportunity to sign a form that would allow them to be contacted by the study staff to learn more about the study. Subjects identified through RPDR will

receive a recruitment letter signed by the PI and the patient's provider (Please refer to the Protocol Summary for additional information). We expect to enroll all patients over a two-year period.

1. SmartPill study and questionnaires regarding gastrointestinal symptoms, quality of life and psychiatric comorbidities (Please see “study procedures” for additional information) will be administered to approximately 50 patients.
2. Histology section – Recruit up to 15 treatment naive patients or patients with less than 6 months of therapy who have lower GI symptoms including abdominal pain and/or bowel movement alterations for which a sigmoidoscopy would be clinically warranted. An endoscopic evaluation with mucosal resection will be performed.

### **SUBJECT ENROLLMENT**

The study will be presented to patients at their regularly scheduled Fabry clinic follow up visit if they report any gastrointestinal symptoms currently or within the past year. If the patient is interested in participation, the consent form will be reviewed by the genetics physician or nurse at the visit and the risks and the benefits of the study will be presented. All questions will be answered. The patient can choose to sign the consent form on the day of the clinic visit, but it is not a requirement. They will be given the opportunity to take the consent form home and decide at a later time if they would like to participate. If the patient does not contact the study staff about the study in a week, the patient will be contacted by the research coordinator. If interested, the research coordinator will schedule the visit with the gastroenterologist. If they choose to sign the consent form on the day of the clinic visit, they will be given the option to complete the screening visit on that day or scheduling the screening visit for a later date within the following 2 weeks.

Patients who have contacted the study staff about the study will be pre-screened by the research coordinator to ensure they meet the criteria. If eligible, they will be provided with an electronic copy of the consent form to review. The email will be sent in accordance with Partners Information Security guidelines. The study staff will provide the patient a couple days to review the consent form before contacting them again to answer any questions they may have about the study. If the patient would like to participate in the study, the research coordinator will schedule a visit with the gastroenterologist.

### **STUDY PROCEDURES**

The study will involve a total of three study visits, with a possibility of a fourth visit. The patient will have the option of signing the consent at their routine Fabry follow up visit or prior to the screening visit. If the patient agrees to participation and signs the consent form, he will be enrolled in the study.

#### **Screening Visit (Visit 1)**

This visit will last approximately 45 minutes. A history and physical will be completed, with particular focus on the gastrointestinal symptoms including gastrointestinal medications and

interventions. Patient will then complete various questionnaires and forms relating to their gastrointestinal symptoms, quality of life and psychiatric issues.

Validated Questionnaires and other data collection – The patient will complete questionnaires including:

1. IBS-QOL (Irritable Bowel Syndrome-Quality of Life)
2. GSRS-IBS (Gastrointestinal Symptom Rating Scale – Irritable Bowel Syndrome)
3. IBS – work productivity/activity impairment
4. Bristol stool chart
5. BDI (Beck Depression Inventory)
6. HAM-A (Hamilton anxiety rating scale )
7. SSI – Symptom Severity Scale
8. GCSI (Gastroparesis Cardinal Symptom Checklist)
9. PAGI-SYM (Patient Assessment of Gastrointestinal Disorders)
10. The Mayo Clinic bowel disease questionnaire

### **Preparation for Study Visit 2**

Prior to the SmartPill study, the subject must remain NPO starting at 10:00pm the night prior to the study initiation. Alcohol is prohibited 8 hours prior to the SmartPill study and throughout the monitoring period. Additionally, tobacco use is prohibited 8 hours prior to initiation and 8 hours after swallowing the capsule. A urine pregnancy test will be completed on any woman of child bearing age as pregnant women are excluded from the study.

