### **SUBJECT SELECTION**

#### **Equitable Selection of Subjects**

This study is open to all individuals, male and female, between 18 and 70 years of age who meet all of the inclusion and exclusion criteria, and have been diagnosed with Fabry disease. Women who are pregnant or nursing will not be allowed to enter the study due to unknown risk factors. Subjects who are not able to provide informed consent form themselves will not be enrolled.

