### **Follow Up Visit (Visit 3)**

This study visit should take about 30-45 minutes to complete and will take place 5 to 7 days after Visit 2.

At this visit, the patient will return the SmartPill receiver and the study diary. We will discuss any questions or concerns they had about the study. If available, we will review the results of the SmartPill test. If it is unclear that the capsule has passed, based on the subject's history or on the study results, we may prescribe erythromycin as a promotility medication or obtain a KUB for verification.

If the patient cannot return the receiver in person, they will be provided with information on mailing the receiver back. Once the results have been reviewed, the patient will be contacted to provide the results of the SmartPill and confirmation of capsule exit.

If the patient is appropriate for the endoscopic mucosal resection, this will be scheduled within the following 3 weeks.

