### **Patients Travelling from Out of State**

Prior to scheduling the visit, the patient will be provided with an electronic copy of the consent form in accordance with Partners Information Security guidelines. They will be advised to read it over. The study staff will then contact the patient after a couple days and answer any questions the patient may have about the study and can be put in contact with the physician. The patient will be notified of all medications that needs to be stopped for the SmartPill and if eligible, for the sigmoidoscopy. All information for the sigmoidoscopy will be sent to the patient and the subject can be put in contact with a physician to answer any additional questions. If the patient agrees, the condensed visit will be scheduled.

The scheduled visit will be a condensed visit consisting of visit 1 and visit 2. The patient will be provided with information regarding mailing the receiver back to the study staff.

If the patient is eligible for the EMR, the visit will be condensed into 2 days. On the first day, the scheduled visit will include the screening visit (visit 1) and the sigmoidoscopy and EMR (visit 4). The patient will be consented by the physician prior to conducting the medical history and physical and completing the questionnaires. After, the patient will be prepped for the sigmoidoscopy and EMR. On the second day, the SmartPill visit will be conducted. This option will also be available for patients who are in state but cannot travel to the hospital multiple times.

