#### **Risks of Endoscopic Mucosal Resection**

Patients enrolled in the study will have one additional low risk procedure (EMR) at the time of their sigmoidoscopy. Patients who warrant a sigmoidoscopy will be asked to participate. Sedation should improve the discomfort of the EMR, but has a risk of complications (primarily low BP, slowed heart rate or respirations) of approximately 1/100. EMR is a common procedure in gastroenterology with a low risk for rectal lesions. In this procedure, one additional small piece of rectal tissue will be obtained for diagnosis.

The risk of one small EMR in the rectum has not been studied in large groups of patients. The risks of EMR in patients with large polyps in the rectum or with large superficial rectal neoplasms vary in the literature. Many smaller studies report no perforations or hemorrhages as a result of EMR. In one large study of EMR for colorectal neoplasia and polyps in 1000 patients, the rate of perforation was 0.2% and bleeding was 2%. **Error! Bookmark not defined.** Large Japanese series with colorectal tumors have reported a perforation rate 0.35% (3/863) and a bleeding risk of 1.16% (10/863) with colonic EMR. **Error! Bookmark not defined.** The risk of one small EMR in the rectum has not been studied in large groups of patients, but presumably has a lower risk than that seen with large resections or piecemeal removal of colonic tumors. There is no psychosocial risk associated with the intervention (EMR). Infants, children age 17 or less, and pregnant or nursing women will not be participating in the trial.

After the procedure, the analysis involves only the pathologic specimens. There is no long-term follow-up of patients for the purposes of this protocol. All enrolled patients will have the same procedure. The intervention in this trial is a one-time event. If a patient does not tolerate sigmoidoscopy or sedation, the procedure may be aborted at the discretion of the endoscopist and

anesthesiologist, in which case the EMR would not be performed. The patients will all receive best standard of care treatment at all times during the study. A patient will be removed from participation in the trial at any time if they request withdrawal.

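### On the two-day path, the study EMR can come before the only pregnancy check that the protocol specifies

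*Combined protocol and SAP*

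**What the plan says.** The exclusion covers the whole study. Equitable Selection of Subjects states: "Women who are pregnant or nursing will not be allowed to enter the study due to unknown risk factors". Risks of Endoscopic Mucosal Resection repeats it for the invasive part: "Infants, children age 17 or less, and pregnant or nursing women will not be participating in the trial". Item 2 of the exclusion criteria names pregnancy alone.

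The one pregnancy test in the supplied text is under Preparation for Study Visit 2: "A urine pregnancy test will be completed on any woman of child bearing age as pregnant women are excluded from the study". That section opens with SmartPill fasting: "Prior to the SmartPill study, the subject must remain NPO starting at 10:00pm the night prior to the study initiation". It names no day for the test.

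Two schedules lead to the EMR.

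- **Standard path.** Visit 3 follows the SmartPill visit by 5 to 7 days, and then: "If the patient is appropriate for the endoscopic mucosal resection, this will be scheduled within the following 3 weeks". The Visit 4 section draws its EMR subset from participants who have already finished SmartPill testing.
- **Two-day path** (Patients Travelling from Out of State, also open to in-state patients who cannot make repeated trips). The order is: "On the first day, the scheduled visit will include the screening visit (visit 1) and the sigmoidoscopy and EMR (visit 4". Then: "On the second day, the SmartPill visit will be conducted".

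**The concern.** An exclusion protects participants only if it is checked before the procedure it is meant to prevent. Here the check is attached to the capsule visit, and one permitted schedule puts the resection before that visit. The protocol calls the capsule's risks minimal. For the EMR visit it gives a sedation complication risk of about 1 in 100. It cites bleeding of 1.16% to 2% and perforation of 0.2% to 0.35% from series of larger resections, and acknowledges that a single small rectal EMR lacks large-scale study. So the test is specified for the lower-risk procedure and not for the higher-risk one.

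If the two-day schedule is followed as written, a pregnant participant could be found ineligible after a resection that cannot be undone. That would be a safety event and an eligibility violation. The assurance in the EMR risk section would then rest on no specified check.

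**Working it through.** **Step 1: where pregnancy status is checked.**

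| Section | What is listed | Test? |
|---|---|---|
| Screening Visit (Visit 1) | History, physical, questionnaires | No |
| Preparation for Study Visit 2 | Urine test, no day named | Yes |
| SmartPill Study Procedure | Start date of last menstrual period, at the ingestion visit | No |
| Sigmoidoscopy and EMR (Visit 4) | Fasting, enemas, procedure | No |
| Patients Travelling from Out of State, day 1 | Consent, history and physical, questionnaires, preparation, sigmoidoscopy and EMR | No |
| Risks of Endoscopic Mucosal Resection | The exclusion restated | No |

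The screening entry begins "A history and physical will be completed, with particular focus on the gastrointestinal symptoms including gastrointestinal medications and" and continues with interventions and questionnaires. It has no laboratory item.

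**Step 2: interval from the SmartPill visit to the EMR.** The documents state no such interval, so there is no figure to reproduce. Because the test has no stated day, the gap is measured from the visit to which it is tied:

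gap = day of EMR − day of SmartPill visit

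- Standard path: (Visit 2 to Visit 3) + (Visit 3 to EMR) = (5 to 7 days) + (0 to 21 days). Minimum 5 + 0 = 5 days; maximum 7 + 21 = 28 days.
- Two-day path: EMR on day 1, SmartPill on day 2, so 1 − 2 = −1 day. The EMR comes first.

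The 28 days assumes that the 3-week limit applies to the date of the procedure and that Visit 3 takes place by day 7. If the receiver is mailed back, no Visit 3 date is set. A test done ahead of Visit 2 would also lengthen the interval from test to EMR.

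**Step 3: how the gap arises.** In the order assumed by the Visit 4 section, a test tied to SmartPill always precedes the EMR. The two-day schedule reverses the order without carrying the test across. The two sections conflict on sequence, and the position of the test is a consequence of that conflict.

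**Step 4: how many patients.** The histology part recruits at most 15. The documents do not say how many will be women of child-bearing age or how many will use the two-day path, so the number affected lies between 0 and 15.

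**Step 5: nursing.** Equitable Selection of Subjects and the EMR risk section bar pregnant and nursing women. The numbered exclusion list names pregnancy only, so someone screening from that list alone would not see the nursing bar.

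**The case against.** The strongest reply is that the text does not stop a site from testing in time. The test has no stated day, its stated reason is the study-wide exclusion, and non-pregnancy is a condition of entry. The two-day path is open only to patients eligible for the EMR. A site that tests on day 1 or before breaks no rule. This stands against one tempting inference, that every woman of child-bearing age on the two-day path has the EMR untested. The documents show only that she can. It does not supply the missing requirement, because day 1 is set out step by step and no test is among the steps.

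Other safeguards exist. The EMR exclusions cover patients for whom sedation or endoscopy is contraindicated, a history and physical precede preparation, and the procedure can be aborted if it is not tolerated. The sigmoidoscopy itself is clinically indicated, so routine care may include a test, and the research addition is the EMR. These reduce the practical risk, but none is stated to include a pregnancy test.

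A reader might also take the interval of up to 28 days on the standard path as an error. It is not one on these documents: they set no validity window for the test, so the interval contradicts nothing.

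Finally, some front matter and the consent pages were removed, and the Protocol Summary mentioned under Recruitment Procedures was not supplied. A test could be specified there, so the claim that there is only one test is limited to the supplied text.

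**Conclusion.** The point holds for the two-day path. The protocol allows, as written, a study EMR one day before the visit that carries its only specified pregnancy check. This is more than missing detail, because two sections give opposite orders for SmartPill and EMR and the check follows only one of them. The finding rests on reading the test as part of SmartPill preparation, which is where the section heading puts it, and on the supplied text being complete on this matter.

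Its reach is small: some of at most 15 patients, in a share the documents do not give. It concerns participant safety and eligibility, and does not bear on the planned regression analyses. The standard-path interval is context only. The nursing omission is a separate, minor inconsistency.

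**What to change.** Reconcile Preparation for Study Visit 2, Follow Up Visit (Visit 3), the Visit 4 section and Patients Travelling from Out of State. The protocol should then state, for each path, when pregnancy status is confirmed relative to the EMR, and the existing check should not be left until after the EMR on the two-day path. The exact timing, and whether any test is repeated, are for the sponsor, the investigator and the IRB to decide.

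In the same amendment, reconcile item 2 of the exclusion criteria with Equitable Selection of Subjects and the EMR risk section on nursing women.

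The cost is a short amendment. On the two-day path the existing urine test would be done earlier, for some of at most 15 EMR patients. Any repeat testing that the sponsor chose to add would be a further cost, not counted here.

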### **SmartPill Capsule Ingestion Visit (Visit 2)**

This study visit should take about 2 hours to complete.

At this visit, the test procedure will be explained to the subject. They will then ingest the SmartBar, a standardized meal used to accurately measure gastric emptying time, within 10 minutes. Following ingestion, the subject will swallow the SmartPill capsule with 70cc of water. They will then receive the SmartPill receiver to carry for the duration of the study, lasting 5-7 days.

During the initial 8 hours after capsule ingestion the subject you will not be allowed to sleep because sleep may affect motility.

The subject will remain NPO for 8 hours after ingestion of the capsule. They will drink a bottle of Ensure 8 hours after ingestion. An hour after drinking the Ensure, the subject can return to their normal eating habits. Instructions will be given to the patient about completion of the daily diary in which they will document periods of ingestion, sleeping patterns and bowel movements in addition to marking it on the receiver. They will also be instructed to wait 5 minutes after each bowel movement to ensure recording of possible passage of the SmartPill.

Prior to leaving, the subject will schedule a follow up visit (visit #3) to return the receiver and the diary and discuss any questions about the study. If the patient has travelled a far distance to participate, they will be given instructions on mailing the receiver and diary back to the office.

After the visit, the subject will keep the receiver at no more than 5 feet from their body at all times during the 5-7 day period. They will be instructed to refrain from any strenuous activities during the study period. The prohibited medications will be reviewed. Additionally, they will again be asked to refrain from alcohol use for the duration of the study.

If the subject is unable to make two visits, they will be given the option to condense the first and second visit into one visit. The visit would last about 2 hours long. Prior to scheduling the condensed visit, the subject will receive an electronic copy of the consent form, in accordance with Partners Information Security guidelines, and will be notified of all medications that need to be stopped for the SmartPill. Any questions will be answered and all information about the SmartPill test will be provided.

The first hour of the condensed visit will consist of the screening visit (visit 1). The subject will be consented by the physician prior to starting the medical history and physical, if not already previously consented during their genetics clinic visit. The subject will be given the opportunity to ask any questions they may have. The subject will also answer the questionnaires during this first hour. If eligible, the second hour of this condensed visit will consist of the SmartPill test (visit 2).

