### *Exclusions Criteria:*

1. Fabry disease with other concomitant gastrointestinal diagnosis (Example: Inflammatory Bowel Disease, Celiac Disease)
2. Pregnancy
3. Endoscopic mucosal resection exclusions:
  - a. Any contraindication to conscious sedation,
  - b. Contraindication to endoscopy,
  - c. Untreated or unmanageable coagulopathy,
  - d. Thrombocytopenia (<50).
  - e. Patient on ERT for more than 6 months.
4. Exclusions for SmartPill:
  - a. Previous history of bezoars.
  - b. Prior GI surgery except for cholecystectomy, appendectomy, or Nissen fundoplication.
  - c. Any abdominal surgery within the past 3 months
  - d. History of diverticulitis, diverticular stricture, and other intestinal strictures
  - e. Tobacco use within eight hours prior to capsule ingestion and during the initial 8-hour recording on Day 0 or the Ingestion visit.
  - f. Alcohol use within eight hours prior to capsule ingestion and throughout the entire monitoring period (5 days).
  - g. BMI > 38
  - h. Allergies to components of the SmartBar
  - i. Use of medical devices such as pacemakers, infusion pumps, or insulin pumps.
  - j. Uncontrolled diabetes with a hemoglobin A1C greater than 10.

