### **ADDITIONAL STUDY INFORMATION**

#### **Description of SmartPill**

The SmartPill GI Monitoring System includes an ingestible capsule, a receiver, a receiver docking station and display software. The capsule houses sensors for pH, temperature, and pressure, and has the ability to transmit the sensed data at 434 MHz to a receiver worn by the subject. The portable receiver worn by the subject receives and stores data; the MotiliGI software provides calculations and graphical displays to the physician. After activation and ingestion, the capsule signals are transmitted from within the GI tract and are captured by a receiving antenna incorporated into the receiver, which also provides an interface for data transmission to a PC as well as connections for battery charging. The capsule functions for at least 5 days after activation and has a pH range of 0.5 to 9 with an accuracy of  $\pm 0.5$  pH units. The pressure sensor has a pressure range of 0 to 350 mm Hg with an accuracy of 5 mmHg. The temperature sensor has a range of 25° to 49°C, with an accuracy of  $\pm 0.8^\circ\text{C}$ .

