### **SmartPill Study Procedure**

Patients taking gastric acid suppressants will be instructed to stop proton pump inhibitors 1 week prior to the colonic transit study and histamine type 2 receptor antagonists 3 days prior to the colonic transit study. Patients with constipation will stop treatments for constipation at least 72 hours prior to the study and for the 5 days of the study. This includes enemas, cathartics, PEG solutions (including Miralax, enulose). Patients with constipation may take medications to help stimulate a bowel movement with either milk of magnesia, 2.4 to 4.8 grams (30-60 ml), or magnesium citrate, 11 to 25 grams daily in 1 or more doses, up to 48 hours prior to SmartPill ingestion.

All study subjects will report for the ingestion visit after an overnight fast (beginning at midnight). Date of the start of the last menstrual period for female subjects will be recorded.

The SmartPill capsule will be activated and calibrated. All study subjects will ingest a SmartBar (a nutritional bar) consisting of approximately 254 calories with 120 cc of water, followed by the SmartPill Capsule with 50 ml of water. The subject may drink an additional 50 ml of water if difficulty swallowing capsule for a total of 100 ml with capsule ingestion. Ingestion of the meal, SmartPill Capsule, and water should be completed within 10 minutes.

Intraluminal GI tract pH, pressure, temperature will be measured continuously with the SmartPill capsule. Once the capsule is ingested the patient is free to leave to the facility. At 8 hours after capsule ingestion, with the subject in a sitting position, one can of regular Ensure (Vanilla, lactose-free, 8 fluid ounces [237 ml]; 250 calories) will be ingested.

All study subjects will maintain a diary and will record times of bowel movements, meals, gastrointestinal symptoms (pain/discomfort, nausea, vomiting), and supine/sleeping times. Subjects will be instructed, if they wish, to recover and return the SmartPill capsule along with the diary and receiver at the end of the study. If they are unable to return to the office due to distance, they will be given material to send the items via FedEx.

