In this study, the exit of the capsule from the GI tract will be confirmed for each subject by examination of the data from the SmartPill study. If the capsule has not passed 5 days after ingestion and confirmation of exit cannot be determined by the SmartPill data, a qualified gastroenterologist will clinically evaluate the study subject and intervene if necessary. Interventions could include use of a laxative to promote capsule transit through the GI tract, endoscopy to retrieve the capsule if within reach of an upper endoscope or colonoscope, or surgical consultation if the capsule appears to be lodged within the small intestine.

Clinical adverse events such as difficulty in device ingestion, vomiting, gastric sensations, and gastric distress shall be assessed during the ingestion day visit. The capsule may fail to empty from the stomach after 8 to 24 hours. The capsule may also fail to pass from the GI tract after 7 days. Subjects ingesting the capsule or the meal may have nausea, vomiting, aspiration of capsule or meal, abdominal pain, diarrhea or constipation.

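### The capsule is recorded for 5-7 days but motility drugs are restricted for only 5, and neither the diary nor the analysis would identify a late exit under a restarted drug

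*Combined protocol and SAP*

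**What the plan says.** All references are to the combined protocol and SAP, which uses two lengths for what appears to be one measurement period.

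**5-7 days.** Under SmartPill Capsule Ingestion Visit (Visit 2): "They will then receive the SmartPill receiver to carry for the duration of the study, lasting 5-7 days", and "the subject will keep the receiver at no more than 5 feet from their body at all times during the 5-7 day period". The same section asks for no alcohol for as long as the study lasts. Follow Up Visit (Visit 3) is set at 5 to 7 days after Visit 2, and the receiver and diary are handed back then or mailed.

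**5 days.** Prohibited Medications for SmartPill: "No medications that affect gastrointestinal motility for 3 full days before the start of the study and during the 5 ensuing days of study". SmartPill Study Procedure: "Patients with constipation will stop treatments for constipation at least 72 hours prior to the study and for the 5 days of the study". The alcohol item in the exclusion criteria gives the whole monitoring period as 5 days. Description of SmartPill: "The capsule functions for at least 5 days after activation".

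**Action on a capsule that has not passed.** The SmartPill Capsule section under Risks and Discomforts provides for clinical evaluation "If the capsule has not passed 5 days after ingestion and confirmation of exit cannot be determined by the SmartPill data". Under Visit 3, if passage is unclear, "we may prescribe erythromycin as a promotility medication or obtain a KUB for verification".

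**Data and analysis.** The diary, as described under Visit 2 and SmartPill Study Procedure, covers meals, sleep, bowel movements and symptoms. Medication is not listed. Biostatistical Analysis plans descriptive statistics and regression on the motility parameters, and says nothing about late exits or about transit recorded after a motility drug.

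**The concern.** The Primary Aim relates gastric, small-bowel and colonic transit to symptoms. The washout exists so that these times reflect the patient's own motility. If the receiver is carried beyond the end of the drug restriction, the last part of the recording has no such protection.

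The patients exposed are those whose capsule is still inside after day 5, so they have the longest transit. They also have a reason to restart: the protocol itself warns that bowel symptoms may worsen during washout. A restarted laxative or prokinetic would shorten the recorded exit time, and a restarted opioid or antidiarrhoeal would lengthen it. The direction of the error is therefore not fixed.

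With no medication entry in the diary and no analysis rule, the analyst would have no planned basis for treating such a time differently from a drug-free one. Without prospectively recorded dose times, the problem could not be reliably repaired afterwards.

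**Working it through.** **1. The plan's own figure.** The Power section argues from 25 patients to 35 to 50: 25 / 0.70 = 35.7 (stated as 35) and 35 / 0.70 = 50. With 5/7 in place of 0.70 the chain gives 35 and 49. The figure of 50 reproduces. It rests on gastric emptying alone, so a problem confined to transit after day 5 does not disturb it.

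**2. The uncovered window.** Inputs: longest recording 7 days (Visit 2, Visit 3); restriction 5 days (Prohibited Medications, SmartPill Study Procedure).
- End of restriction: 5 x 24 = 120 h.
- End of longest recording: 7 x 24 = 168 h.
- Uncovered: 168 - 120 = 48 h, or 48 / 168 = 29% of a 7-day recording.
- If the receiver is returned on day 5: 0 h.

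The 29% is clock time. It is not a share of patients or of transit data.

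**3. Which values can be affected.** A drug restarted after the restriction ends is taken after 120 h, so a recorded exit under that drug lies between 120 and 168 h. The drug-free exit time is unknown, but it too exceeds 120 h. The patient therefore ranks above everyone who passed the capsule within 5 days, with or without the drug. Only the exact value, and the order among exits beyond 120 h, is in doubt. Under any slow-transit cut-off at or below 120 h (an assumption; the documents state no cut-off) nobody changes category. Gastric emptying is reached only if the capsule is still in the stomach after day 5. The risk section cites one such case, at 9 days, from earlier studies.

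**4. How many patients.** The documents give no share q with the capsule inside beyond day 5, so q is assumed. Expected number = 50q; chance of at least one = 1 - (1 - q)^50.

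| Assumed q | Expected of 50 | Chance of at least one |
|---|---|---|
| 2% | 1 | 64% |
| 5% | 2.5 | 92% |
| 10% | 5 | 99% |

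These are upper bounds. To be affected, the patient must also keep the receiver past day 5, restart a drug before exit, and have a capsule that still transmits, and the stated function is only at least 5 days.

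**5. Whether investigator-prescribed treatment overlaps the recording.** Erythromycin is considered at Visit 3, when the receiver is handed back. If the receiver is mailed, the patient is contacted after the results have been reviewed. The laxative and other interventions in the risk section require both no passage at 5 days and SmartPill data that do not establish exit, so the data have been read. On the schedule as written the overlap is nil.

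**The case against.** The strongest reply is that 5 days is the real measurement period. The alcohol exclusion, both drug restrictions, the stated capsule function and the trigger for evaluating a retained capsule all use 5 days. The 5-7 days would then be slack for returning the receiver. This is a reasonable guess at the intent, but the text does not say it: Visit 2 makes 5-7 days the length of the study and requires the receiver to stay close to the body throughout. No section says that data after day 5 are disregarded.

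Three further objections stand and limit the point:
- A reader might infer from the day-5 evaluation and the erythromycin provision that the study records transit under treatment its own investigators prescribe. The documents do not support that, because such treatment follows return or reading of the receiver.
- A reader might also suppose that recording continues until a mailed receiver arrives. Visit 2 limits carrying to 5-7 days.
- It would be too strong to say that the slow tail becomes a drug effect. Affected patients have already gone 120 h under restriction and remain in that tail. The documents also give no figure for how much of any symptom-motility association those patients carry.

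Analysing such exits as lower bounds has its own weakness. A patient may take a drug because transit is slow, so censoring at the dose can be informative.

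**Conclusion.** The point holds as a minor inconsistency in a rule that governs the primary motility measurement. Recording can outlast the drug restriction by up to 48 h, and a patient who restarts their own motility drug in that window breaks no written rule. The diary does not ask for it and the analysis does not provide for it. That the resulting time would be treated as an ordinary one is an inference from the absence of a rule; the plan does not say so.

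The consequence is confined to the exact values of colonic and whole-gut times already above 120 h. It probably concerns few patients: at most 1-5 of 50 if 2-10% retain the capsule beyond day 5, a range that is assumed. Gastric emptying and the sample size are essentially unaffected. Because function beyond day 5 is not guaranteed, exit times that are never recorded are at least as likely a problem as drug-affected ones, and one analysis rule can serve both.

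**What to change.** 1. Reconcile the exclusion criteria, Prohibited Medications, Visit 2, Visit 3, SmartPill Study Procedure and The SmartPill Capsule risk section so that the recording period and the restriction period agree, for alcohol as well as for drugs. Which length applies is the sponsor's decision.
2. Add to the diary the date and time of any motility-affecting drug taken until the receiver is returned.
3. Pre-specify one rule in Biostatistical Analysis: an exit after the end of the drug-restricted period, or after a motility drug is taken, is analysed as greater than that time (the earlier of the two), either censored or given the top rank, and not as an exact transit time.
4. Because censoring at a dose may be informative, report a sensitivity analysis that uses the recorded times.

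The cost is consistent wording in six sections, one diary line and one analysis rule. A few exact times become lower bounds. Clinical handling of a retained capsule is unchanged.
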